8.9 QUALITY OF LIFE OR PHARMACOECONOMIC ENDPOINTS AND ANALYSES

For the Quality of life questionnaire see subsection 'Tertiary efficacy endpoints' in Section 8.7.2.

8.10 SAFETY DATA ENDPOINTS AND ANALYSES

All Safety analyses will be performed on the Safety Population.

8.10.1 Adverse Events (AEs)

All AEs will be coded using MedDRA dictionary. The version of the dictionary will be provided in the adverse events tables, figures and listing footnotes.

All information on AEs will be listed by subject.

Treatment-Emergent Adverse Events (TEAEs) will be defined as AEs that started on or after the date of the first dose of the received treatment.

AEs that occurred prior to the first dose of the received treatment and increased in severity and/or relationship after the first dose of the received treatment will also be regarded as TEAEs. If it is not possible to determine whether an AE is a TEAE due to a missing start date, the AE will be regarded as a TEAE unless the stop date indicates that the AE occurred prior to the first dose of the received treatment.

All reported TEAEs will be summarized.

The number and percentage of subjects experiencing the following categories of AEs will be summarized for each received treatment group and for all received treatment groups combined both overall and by system organ class and preferred term:

- TEAEs
- Related TEAEs
- Serious TEAEs
- Related and serious TEAEs
- TEAEs leading to study drug discontinuation
- TEAEs leading to study drug interruption
- Non-TEAEs

In addition, the number and percentage of subjects experiencing the following categories of AEs will be summarized for each received treatment group and for all received treatment groups combined by system organ class, preferred term and maximal severity:

- TEAEs
- Related TEAEs

For all system organ classes and preferred terms with a TEAE incidence rate of at least 5% over all received treatment groups combined, the number and percentage of subjects will be summarized for each received treatment group and for all received treatment groups combined by system organ class and preferred term.

Subjects will be counted only once within each system organ class, preferred term and severity.

- If a subject has experienced more than one adverse events coded within the same system organ class then this subject will be counted only once within that system organ class.
- If a subject has experienced more than one adverse events coded to the same preferred term within a system organ class then the subject will be counted only once for that preferred term and within that system organ class.
- If a subject has experienced more than one adverse events coded to the same preferred term within a system organ class then the subject will be counted only once under the

maximum severity for that preferred term and within that system organ class. The maximal severity is defined as first death (the highest possible level of severity), then life-threatening followed by severe, moderate, and mild (the lowest possible level of severity).

If a subject has experienced any AE with a missing severity then the AE's grade will be imputed as the maximal reported grade over all AEs experienced by that subject (excluding death). If a subject has experienced any AE with a missing relationship then the AE's relationship will be assumed to be related to study drug.

Adverse Events of Special Interest (AESI)

Potential effect of GKT137831 on arterial blood pressure and its clinical relevance will be evaluated. Systolic and diastolic blood pressure values will be examined together with temporally associated blood pressure related events including adverse events and serious adverse events, changes in study drug administration and other related changes in concomitant medications.

Drug induced liver injury related events will be considered as AESI as well.

In addition, the medical history and other possible contributing risk factors will be assessed.

The following categories of AEs will be listed by subject:

- All adverse events
- All TEAEs
- All serious AEs
- All AEs leading to study drug discontinuation
- All AEs leading to study drug interruption
- All AEs leading to death
- All AESI

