6.4 VISIT WINDOWING

Visit windowing will be considered only for efficacy and pharmacodynamic assessments.

The halfway point corresponding to the visits will be considered in relation to the date of first dose. Efficacy assessments are planned to be conducted at Week 2, Week 6, Week 12, Week 18, Week 24 and Week 28 visits. The following windowing rules will be taken into account to establish the visit corresponding to each efficacy and pharmacodynamic assessment:

- Week 2: any efficacy or pharmacodynamic assessment performed between 2 to 28 days after the first dose;
- Week 6: any efficacy or pharmacodynamic assessment performed between 29 days to 63 days after the first dose;
- Week 12: any efficacy or pharmacodynamic assessment performed between 64 days to 105 days after the first dose;
- Week 18: any efficacy or pharmacodynamic assessment performed between 106 days to 147 days after the first dose;
- Week 24: any efficacy or pharmacodynamic assessment performed between 148 days to 182 days after the first dose;
- Week 28: any efficacy or pharmacodynamic assessment performed between 183 days to 203 days after the first dose;

If two (or more) assessments are recorded within a visit window, the closer (closest) to the halfway point will be taken into account for the analyses. If two assessments within a visit window are the same number of days from the halfway point, the second one will be taken into account for the summaries assuming that it is more reliable than the first one.

No programmatic windowing of visits will be considered for safety data. Post-baseline data will be presented according to the visit at which it was collected on the eCRF or as described in this SAP.

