6.6 REPORTING GUIDELINES

The following guidelines will be followed:

- Page Orientation: Landscape.
- **Post-text tables and listings**: will be generated in .lst and converted to rtf.
- **Post-text figures**: will be generated directly in .rtf.
- **Font**: Courier New font with minimum of 9 points font size.
- Margins: Left: 3.8 cm, Right: 2 cm, Top: 3 cm, Bottom 2 cm on A4 paper.
- Columns headers will be left aligned.
- **Treatment labels** will be the following and displayed in the following order, unless otherwise stated:
 - o GKT831 400mg OD
 - o GKT831 400mg BID
 - o Placebo
 - o **Total**
- Visit labels: the visit labels displayed in Table 1 will be used as required.

Table 1: Visit Labels

Study Stage	CRF Visit	Tables, Figures and Listings Label
Screening	Visit 1 (Screening): Day -28 to -7	SCR
	Visit 2 (Baseline): Day 1	BAS
	Visit 3: Week 2 +/- 3 days	TRT W2
Treatment phase	Visit 4: Week 6 +/- 3 days	TRT W6
Treatment phase	Visit 5: Week 12 +/- 3 days	TRT W12
	Visit 6: Week 18 +/- 3 days	TRT W18
	Visit 7: Week 24 +/- 3 days	TRT W24
Follow-up phase	Visit 8: Week 28 +/- 3 days	FU W28

- Unscheduled visit / repeat assessments: Data obtained at unscheduled or repeat assessments will be taken into account in baseline determination and efficacy summaries based on windowed visits. All other data from unscheduled or repeat assessment will not be included in summaries but only be presented in data listings, unless otherwise specified.
- **N:** The number of subjects in the specified population.
- **Treatment presentation:** The summaries will be presented by allocated or actual treatment group (see more details in Section 7) and overall for disposition, demographics and baseline characteristics, protocol deviations, concomitant medications, study drug exposure and compliance.
- **Continuous data** will be summarized using number of subjects (n), mean, standard deviation (SD), median, minimum value, maximum value and number of missing data (if there are any).
- **Categorical data** will be summarized using n and percentage based on number of nonmissing data.
 - All categories will be presented, even if no subjects are counted in a particular category.
 - In case 1 or more subjects have missing data for the summary, the number of missing data will be presented as a separate category, labelled accordingly as 'Missing', if not otherwise stated.
 - Counts of zero in any category will be presented without percentage.

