 - For AEs, medical history, prior and concomitant medications the counts are based on single counts of subjects with multiple events/treatments under same category, while the percentages are calculated using N.
- Precision of summary statistics:
 - Integer Sample size (n, N) and number of missing data (if displayed);
 - One additional decimal place than reported/collected mean, median, other percentile, confidence interval;
 - Two additional decimal places than reported/collected standard deviation;
 - Same number of decimal places as reported/collected minimum, maximum;
 - Percentages one decimal place.
- **Study day** for an assessment will be calculated with reference to the date of first dose as Day 1.

This will be calculated as follows:

(assessment date - date of first dose) + 1 if the assessment date is on or after the date of first dose,

(assessment date - date of first dose) if the assessment date is prior to the date of first dose.

- Data will be presented in listings by allocated treatment group. The order will be subject ID, visit, assessment date/time and assessment type/parameters (in the order collected on e-CRF, unless otherwise specified). For clinical laboratory results, the listings will be presented in the order of allocated treatment group, subject ID, parameter, assessment date/time, visit.
- Dates will be presented in format DD-MMM-YYYY.
- Version 4.03 of the NCI-CTC grading criteria (CTCAE v4) will be used for relevant tables [3].
- Latest version of the Medical Dictionary for Regulatory Activities (MedDRA) will be used for the adverse events coding. The version will be specified in the footnote of the corresponding TFLs.
- Latest version of the WHO-DRUG dictionary will be used for the medications coding. The version will be specified in the footnote of the corresponding TFLs.
- File naming: The name of each TFL output file will start with a t (for a table), f (for a figure) or I (for a listing) to denote the output type and will include an appropriate numbering as well as a reference to the associated domain and analysis set.

7 Analysis Sets

The following populations will be considered in the data analysis:

Randomized population

The Randomized population will include all subjects randomly allocated to a treatment arm. The Randomized population will be analysed by the allocated treatment group.

Intent-To-Treat (ITT) population

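### Read literally, the SAP can leave unscheduled and re-test liver values out of the by-arm worst-grade tables, and it plans no by-arm count of the joint liver criterion or of grouped DILI events

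*SAP*

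**What the plan says.** **Adverse events (SAP 8.10.1).** Seven categories are counted by received treatment: all TEAEs, related, serious, related and serious, leading to discontinuation, leading to interruption, and non-TEAEs. The special-interest paragraph then adds liver injury to blood pressure: "Drug induced liver injury related events will be considered as AESI as well". The output named for special-interest events is the last item in a list introduced by "The following categories of AEs will be listed by subject".

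**Laboratory data (SAP 8.10.2).** Abnormality incidence, shifts and worst CTCAE grade are given by arm, one parameter at a time.

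**Which values count (SAP 6.4 and 6.6).** Repeat values are admitted to baseline and efficacy: "Data obtained at unscheduled or repeat assessments will be taken into account in baseline determination and efficacy summaries based on windowed visits". For everything else: "All other data from unscheduled or repeat assessment will not be included in summaries but only be presented in data listings, unless otherwise specified". SAP 6.4 adds: "No programmatic windowing of visits will be considered for safety data".

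**Protocol.** Section 6.3.1 interrupts dosing on set liver triggers and calls for a re-test within 2 to 3 days. It then names one case for permanent discontinuation: a re-test ALT or AST at least 3 times baseline and above the ULN, together with new bilirubin of at least 2 x ULN or INR of at least 1.5. Section 10.4.3.8 allows a repeat or unscheduled laboratory result into the summary tables when it is the one nearest the planned day.

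**The concern.** The protocol treats the liver as a specific risk. Section 2.3 expects drug to accumulate in liver tissue and says the incidence of DILI will be watched, and the safety objective in section 3 is a comparison with placebo. The values that decide whether a subject has suspected DILI are mostly re-test values, taken between planned visits. If these go only to listings, the by-arm worst grade may not be the worst grade observed.

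The joint criterion also depends on two abnormalities in the same subject, which single-parameter tables cannot show. And if liver cases are coded to several preferred terms, no row of the adverse event tables adds them up. At stake is whether the study report shows the arms side by side on the liver outcome the protocol itself defines.

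**Working it through.** The plan gives no DILI rate or liver count to reproduce. The only design figures needed are 34 per arm and 102 in total (SAP 5.4). The 80% power stated for that size reproduces at 79.8% (Wilcoxon Mann-Whitney, 20,000 simulated trials, normal data, difference 28, SDs 30 and 40, alpha 0.023475). Nothing below changes it.

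**1. Do re-test values reach the worst-grade tables?**
- SAP 6.6 sets the default: unscheduled and repeat safety values are listed and not summarised, unless a section says otherwise.
- SAP 8.10.2 makes no exception and does not say which values feed the worst grade.
- SAP 8.10.4, by contrast, expressly limits the worst QTc change to planned visits. One could infer that 8.10.2, being silent, is meant to be wider. The default in 6.6 points the other way.
- Example built from the 6.3.1 thresholds: bilirubin reaches 1.5 x ULN at a planned visit while ALT is below 5 x ULN. Dosing is interrupted, and the re-test ALT is 5 x ULN or more. The grade 3 ALT exists only in the re-test. Under the literal reading it is absent from the worst-grade table.
- Protocol 10.4.3.8 is wider, because a repeat nearest the planned day would be used. It still takes one value per visit, so it does not guarantee the peak either. SAP section 10 lists only the two-stage final analysis as a change.

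**2. Is the joint criterion counted?** It appears nowhere in the SAP, and neither does its multiple-of-baseline element. Single-parameter tables cannot recover it. Take one arm of 34:
- Subject A has raised ALT and subject B has raised bilirubin: ALT row 1/34, bilirubin row 1/34, joint 0/34.
- Subject A has both: ALT row 1/34, bilirubin row 1/34, joint 1/34 = 2.9%.

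The planned rows are identical in the two cases.

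**3. Is DILI grouped by arm?** Special-interest events are in 0 of the 7 by-arm categories and 1 of the 7 listing categories. Two cases coded to different terms show as two rows of 1/34 = 2.9%, where a grouped row would show 2/34 = 5.9%. Adding rows is not safe, because de-duplication works within a class ("then this subject will be counted only once within that system organ class") and a subject may have terms in more than one class. A hand count from listings is possible, but "Data will be presented in listings by allocated treatment group", whereas the safety tables use received treatment, so the two could differ if anyone received the wrong treatment.

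**4. Precision of any added row.** With 0 of 34, the exact two-sided 95% upper limit is 1 − 0.025^(1/34) = 10.3%.

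**The case against.** The strongest reply is that much of this is already visible by arm, and several parts of that reply stand.

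- **Disposition.** SAP 8.1 counts reasons for treatment discontinuation by allocated arm, and the disposition table is among the top-line outputs. Protocol 5.6.4 makes confirmed or suspected DILI its own mandatory withdrawal reason, and 5.6.5 has the primary reason recorded. If the eCRF reasons follow 5.6.4, this table already counts DILI withdrawals by arm. If the eCRF offers only a general adverse-event reason, it does not. The eCRF is not among the documents.
- **Adverse event tables.** Protocol 9.2.1.3 turns laboratory findings that stop or hold dosing into adverse events, so DILI stops reach the discontinuation and interruption tables by coded term.
- **Triggers.** The laboratory triggers for interruption in 6.3.1 are written as CTCAE grades, and INR is in the hematology panel (protocol 8.2.1). The worst-grade tables therefore largely match them, and a separate trigger-by-component table is not needed.
- **Efficacy summaries.** Re-test ALT, AST and bilirubin can enter the windowed efficacy summaries, where "the closer (closest) to the halfway point will be taken into account for the analyses". That gives one value per window, by allocated arm, one parameter at a time and without INR.

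A reader might infer that no planned output shows DILI by arm. The documents do not support that, for the reasons above. A reader might also infer that subjects are less well protected. They are not: 6.3.1 applies in full, and protocol 9.7 makes a permanent stop for DILI a trigger for an SMB meeting.

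In the other direction, the protocol's statement in 10.4.3.4 that special-interest results are shown by treatment group sits in a paragraph about blood pressure. The SAP does not repeat it, so it does not close the gap for DILI.

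**Conclusion.** The point holds as a minor gap in final safety reporting, worth correcting because it is cheap. Three things stand on the text: SAP 6.6, with no exception in 8.10.2, can keep peak and re-test liver values out of the by-arm worst grade; no planned table counts the joint 6.3.1 criterion; and grouped DILI events have no by-arm row. The first carries the most weight, since it is a stated rule that can understate liver findings and is an undeclared narrowing of the protocol. The grouped row alone would be close to a reporting preference.

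The size cannot be put as an expected number of subjects, because the documents give no liver event rate. Per subject affected it is 2.9 percentage points in an arm of 34. The conclusion assumes that 6.6 is read as written and that no table shell outside these documents adds the missing rows. Alpha, power and the efficacy analysis are unaffected.

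**What to change.** 1. In SAP 8.10.2, as a stated exception to 6.6, derive the worst CTCAE grade from all post-dose results, including unscheduled and 6.3.1 re-test values. Record the departure from protocol 10.4.3.8 in SAP section 10.
2. Add one descriptive n (%) row by received treatment for the joint 6.3.1 criterion, using the same values.
3. In SAP 8.10.1, add special-interest events to the by-arm categories, with DILI grouped across preferred terms and system organ classes, and state which events belong to the group.

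No test is needed. The cost is SAP wording and a few sparse rows. Counts will be small and need cautious reading. Protocol 6.3.1 allows local re-tests, so those results need their own ULN and must reach the database. Subjects on anticoagulants may enter with INR above 1.2 and need a flag in the INR component. The liver report form goes to the CRO safety group (protocol 9.5), so the grouped row may need reconciling with the clinical database.

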8.10.2 Clinical Laboratory Evaluations

Laboratory parameters (hematology, biochemistry, TSH levels, urinalysis) results and changes from baseline will be summarized with descriptive statistics by visit for each received treatment group and for all received treatment groups combined.

The changes from baseline will also be displayed by visit for each received treatment group using box plots.

For each laboratory parameter, the incidence of abnormal results (i.e. outside of the normal range) will be summarized by visit for each received treatment group and for all received treatment groups combined. For dipstick parameters with a categorical response, any positive result will be considered abnormal.

For each parameter, the shift from baseline to each planned post-baseline visit in the range of values (low, normal, high and abnormal [low/high]) will be summarized by post-baseline visit with the number and percentages of subjects.

For the calculation of descriptive statistics, all laboratory results will be converted to SI units. Differential counts will be presented both as absolute values and as percentages of white blood cells.

The NCI-CTCAE criteria v4.0 [3] will be used to determine severity.

Template Author: [name] Version 3.0 16AUG2017

For each hematological parameter, the number and percentage of the worst NCI-CTCAE grades will be presented for each received treatment group. The shift from baseline grade to the worst NCI-CTCAE grade will also be presented by received treatment group for each hematological parameter.

For each biochemistry parameter, the same summaries on the worst NCI-CTCAE grades will be produced.

All data will be listed in subject data listings and abnormal results will be flagged.

The laboratory parameters assessments reported as '<LOQ' will be imputed with and displayed as the calculated value equal to LOQ/2 in the listings.

8.10.3 Vital Signs

Vital signs include Pulse rate, Systolic Blood Pressure (SBP) and Diastolic Blood Pressure (DBP). Pulse rate, SBP and DBP values as well as change from baseline to each planned visit will be summarized with descriptive statistics by visit for each received treatment group and for all received treatment groups combined.

The shift from baseline to each planned post-baseline visit for each of the criteria specified in Table 2 will be summarized by post-baseline visit for each received treatment group and for all received treatment groups combined.

Vital Sign	Criteria	Flag
	< 55 bpm	Low (L)
Pulse Rate	≥ 55 to ≤ 100 bpm	Normal
	> 100 bpm	High (H)
	< 90 mmHg	Low (L)
Systolic Blood Pressure	≥ 90 to ≤ 140 mmHg	Normal
	> 140 mmHg	High (H)
	< 45 mmHg	Low (L)
Diastolic Blood Pressure	≥ 45 to ≤ 90 mmHg	Normal
	> 90 mmHg	High (H)

Table 2: Vital sign values of clinical importance

Box plots will be produced to plot the vital signs change from baseline at each visit.

Vital signs (including Body Weight) will be listed by subject and visit with both conventional and Standard International values and all results considered abnormal as per criteria defined in Table 2 will be flagged.

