The dog was the most sensitive species and the NOAEL was established at 150 mg/kg/day in the 26 week study. Treatment related effects in the dog studies were confined to ECG changes, effects on thyroid hormones, and effects on hematology parameters/bone marrow. Changes in liver function tests observed were generally considered to be of minimal severity and reversible and led to no liver pathologies and are consequently not considered to be of toxicological relevance. In the 28 Day study, QTc(F) prolongation was observed in high dose dogs (1000 mg/kg) and there was a single animal with an AV-block. The QTc prolongation was observed at both measurement times (Day 1 and Day 23) but the increase at the Day 23 reading was limited and seemed to affect only 2/6 treated high dose animals. Although there were no such ECG alterations observed in the 13 Week study, measurements in high dose dogs taken at Week 1 and 4 of the 26 Week study (animals still on 500 mg/kg/day) showed QTc (VdeW) increases of up to 20 msec. There were no QTc prolongation observed after the dose reduction to 300 mg/kg/day at week 13 and 26. The absence of any clear treatment-related ECG alterations at both the NOAEL of 150 mg/kg/day and the HTD (Highest Tolerated Dose) of 300 mg/kg/day in the 26 Week dog study and in already conducted clinical trials suggest that any such liability will not compromise subject safety in early stage clinical studies. Effects on bone marrow were seen at 500 mg/kg/day, the highest dose tested in the 26 week study and in one animal resulted in a severe non regenerative anemia which lead to euthanasia. Effects were restricted to the erythroid lineage and were preceded by a marked reduction in reticulocytes indicating the potential to monitor any potential effect in the clinic.

Reproductive toxicology studies have been performed in rats and rabbits. No treatment-related embryo-fetal findings in any dose group were seen in rats at doses of up to 1000 mg/kg/day. The NOAEL for maternal toxicity was established at 1000 mg/kg/day and for embryo-fetal toxicity was 300 mg/kg/day. In rabbits, GKT137831-related maternal mortality and severe effects on food consumption and body weight were seen at 1000 mg/kg/day, but there was no evidence of embryo-fetal toxicity at any dose level. The NOAEL for maternal and embryo-fetal toxicity was considered to be 300 mg/kg/day.

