	Optionally, assessment of metabolomics signatures.
	Optionally, assessment of additional biomarkers of interest.
SECONDARY OBJECTIVES:	• Subjects with AEs from starting IMP to 28 days after the last administration.
To evaluate the safety of oral GKT137831 in comparison with placebo, in subjects with PBC.	• Clinical laboratory evaluations at Screening, baseline/Day 1 and Weeks 2, 6, 12, 18, 24 and 28.
	• Urinalysis at Screening and Weeks 12, 24 and 28.
	• Thyroid stimulating hormone (TSH) measured at baseline/Day 1 and Weeks 12 and 24.
	• Pulse rate, SBP and DBP at Screening, baseline/Day 1 and Weeks 2, 6, 12, 18, 24 and 28.
	Body weight at baseline/Day 1 and at Week 24.
	• 12-lead ECG during Screening and at Weeks 2, 12, and 24.
To estimate the population pharmacokinetics (PK) of GKT137831 and explore any potential PK-PD relationships	• Plasma concentrations of GKT137831 and its main phase 1 metabolite, GKT138184.
	The plasma concentrations will be subjected to population PK analysis to estimate population PK parameters such as clearance and volume of distribution and associated inter-individual variability

Protocol No.: GSN000300	Compound No.: GKT137831
Protocol Version No.: Final 4.0; Amendment 3	Sponsor: Genkyotex
Protocol Date: 24 July 2018	Author: Cmed Clinical Services

in this subject population.	(IIV), and to determine predictors of IIV.
	PK-PD analysis will be carried out using the primary endpoint and selected secondary endpoints in order to explore any potential PK-PD relationships. Exploratory Endpoint:
	• Additional biomarkers of interest will be measured in plasma or serum. The identity of these exploratory markers will be defined in response to findings described in the literature or obtained in this study. These markers will not have diagnostic or prognostic value and will not have an established normal range according to the World Health Organization (WHO).
To explore any relationship between genetic parameters and therapeutic responses in a subset of subjects.	• Genetic and pharmacogenetic research may be conducted on the DNA samples collected at baseline/Day 1 from subjects who sign an optional, additional informed consent. In particular, the impact of polymorphisms in the NOX1 and/or NOX4 genes on pharmacodynamic and therapeutic responses may be assessed.

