#### Vital Signs and Body Weight:

Pulse rate, SBP, DBP and body weight will be summarized using descriptive statistics by treatment group and planned visit.

Both the absolute values and the change from baseline will be considered.

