The interim analysis will be conducted by the unblinded SMB statistician, who has no involvement with the study conduct. The interim analysis outputs will be communicated to the Sponsor's Chief Medical Officer.

The interim analysis described above does not include assessments of safety data. The safety data will be reviewed periodically and separately as described in the study SMB charter.

10 Changes to Planned Analyses

The final analysis will be performed according to a 2-stage process detailed in Section 6.1.

11 Document History

Date	Version	Modified by	Brief details of changes made to template
150CT2018	1.0	[name]	Initial final version
15MAR2019	2.0	[name]	Updated final version The main changes are the following: 1. Addition of Section 6.1 to clarify the timing of the final analysis. 2. Addition of Appendix 1 to provide the list of Top Line tables.

12 References

[1] New Drug Application (NDA) 207999 submitted by Intercept Pharmaceuticals, Inc. for obeticholic acid (OCA) proposed for the treatment of Primary Biliary Cirrhosis (PBC), Gastrointestinal Drug Advisory Committee (GIDAC) Meeting, April 7th, 2016.

[2] Hirschfield GM et al. Efficacy of Obeticholic Acid in Patients With Primary Biliary Cirrhosis and Inadequate Response to Ursodeoxycholic Acid. Gastroenterology 2015; 148: 751-761.

[3] CTCAE v4.03:

http://evs.nci.nih.gov/ftp1/CTCAE/CTCAE_4.03_2010-06-14_QuickReference_5x7.pdf

13 Appendix 1: List of Top Line tables

Table order	Table number	Table title
1	14.1-1	Subject Disposition (Randomized Population)
2	14.1-3	Summary of Demographic and Baseline Characteristics (ITT Population)
3	14.1-5.1	Disease Characteristics (ITT Population)
4	14.2-1.1.1	Summary of Absolute and Percent Change from Baseline to Week 24 Visit in Serum GGT (ITT Population)
5	14.2-1.1.2	Analysis of Percent Change from Baseline to Week 24 Visit in Serum GGT (ITT Population)
6	14.2-1.3.1.1	Summary of Percent Change from Baseline to Week 24 Visit in Serum GGT by Subgroup of Baseline GGT values (ITT Population)
7	14.2-1.3.1.2	Analysis of Percent Change from Baseline to Week 24 Visit in Serum GGT by Subgroup of Baseline GGT values (ITT Population)
8	14.2-2.1.1	Summary of Absolute and Percent Change from Baseline to each Post- Baseline Visit in Serum GGT (ITT Population)
9	14.2-2.1.2	Analysis of Percent Changes from Baseline in Serum GGT across all Post Baseline Visits [a] Model Estimates (ITT Population)

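### The SAP drops the protocol's by-arm summary of body-weight change, leaves post-baseline weight in a subject listing only, and does not declare the difference

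*SAP*

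**What the plan says.** **Protocol.** Section 3 lists "Body weight at baseline/Day 1 and at Week 24" among the outcome measures for the safety objective, which is framed as a comparison with placebo. Section 10.4.2.5 repeats body weight as a safety endpoint, and Section 7.5 adds a measurement at the Early Termination visit. The analysis commitment is in Section 10.4.3.4: "Pulse rate, SBP, DBP and body weight will be summarized using descriptive statistics by treatment group and planned visit", followed by "Both the absolute values and the change from baseline will be considered".

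**SAP.** Section 8.10.3 opens with "Vital signs include Pulse rate, Systolic Blood Pressure (SBP) and Diastolic Blood Pressure (DBP". It then states which measures are summarised: "Pulse rate, SBP and DBP values as well as change from baseline to each planned visit will be summarized with descriptive statistics", by visit and received treatment group. The shift criteria in SAP Table 2 cover the same three measures. Weight enters the section only in the listing sentence: "Vital signs (including Body Weight) will be listed by subject and visit". Section 8.3 includes weight and BMI among the baseline characteristics summarised by allocated arm. Section 10, on changes to the planned analyses, contains one item: "The final analysis will be performed according to a 2-stage process detailed in" Section 6.1.

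**The concern.** The protocol and the SAP disagree about what is produced for a named safety endpoint, and the SAP is the document from which tables are programmed. Its introduction says that it sets out the methods, derivations and summaries to be used, and it cites the same protocol version (4.0, Amendment 3) that contains the promise. If the SAP is followed as written, the study report will show how heavy each arm was at entry but will not show, by arm, what happened to weight over 24 weeks.

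A by-subject listing does not replace that summary. It gives individual rows for about 100 subjects, with no mean, spread or change by arm. A modest shift in average weight on one dose is hard to see in such a listing and easy to see in a small table.

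**Working it through.** The plan gives no figure to reproduce here, and the point needs no arithmetic. The check is to set each output that the protocol implies for body weight against every place where the SAP deals with weight or vital signs.

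| Body-weight output | Protocol | SAP |
|---|---|---|
| Baseline value, by arm | Promised (10.4.3.4) | Planned (8.3, ITT population, allocated arm) |
| Week 24 value, by arm | Promised (10.4.3.4) | Not planned |
| Change from baseline to Week 24, by arm | Promised (10.4.3.4) | Not planned |
| Early Termination value | Measured (7.5); no specific summary rule | Listing only |
| Subject listing | Not specified | Planned (8.10.3) |
| Difference declared | n/a | No (Section 10) |

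Of the three by-arm outputs promised, one is planned, and it is the one that carries no information about a drug effect.

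Other places in the SAP that might supply the missing summary:

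1. **Box plots (8.10.3).** These plot the change from baseline in vital signs. The section's own definition of vital signs leaves weight out, no split by arm is stated, and a plot is not a table of descriptive statistics.
2. **Listings (6.6).** These are ordered by allocated treatment group, so a reader can find each arm's rows. They contain no summary statistics, whereas the safety summaries elsewhere are by the treatment actually received.
3. **Top Line tables (Appendix 1).** No weight table appears. The list holds only disposition, baseline and efficacy tables, so this absence says little either way.
4. **Adverse event tables (8.10.1).** Protocol Section 9.2.1.3 says that objective measurements should not routinely be recorded as adverse events. The exceptions are those that meet seriousness criteria, lead to study drug being stopped or withheld, or need medical intervention. A modest average change in weight would therefore not normally reach these tables.

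On Early Termination values, SAP Section 6.4 applies no visit windows to safety data and presents results under the visit at which they were collected. Protocol 7.5 places these values on their own eCRF page, and SAP Table 1 has no label for that visit. A by-visit weight table would therefore not pick them up unless the SAP says so.

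**The case against.** The best case for the SAP is that this is loose drafting. The listing sentence treats weight as a vital sign, so the author may have meant it to be included throughout 8.10.3, box plots too. The full list of planned tables is not in the documents, and Section 6.1 refers to further outputs beyond the Top Line set. Baseline weight is summarised by arm, and listings are grouped by arm. What stands is that the two sentences in 8.10.3 are inconsistent and that the raw data are not lost. What does not stand is any claim that the promised summary is planned: the sentence governing the summary names three measures, and weight is not one of them.

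A reader might also infer more than the documents support:

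- **That a toxicity signal is being left unexamined.** Protocol Section 2.1.4 does report "maternal mortality and severe effects on food consumption and body weight were seen at 1000 mg/kg/day", but this was a rabbit reproductive study at a dose that also killed dams, with a stated no-effect level of 300 mg/kg/day. The dog effects named as treatment-related were on ECG, thyroid hormones and blood or bone marrow. Protocol Section 2.3 singles out liver injury and anaemia, not weight.
- **That power to detect a weight difference is lost.** The documents give no standard deviation for weight change, and the protocol plans neither a test nor a confidence interval for it. Such figures would rest on an assumption and would describe outputs that nobody promised.
- **That the protocol requires an adjusted comparison with placebo.** It promises descriptive statistics only, and no safety measure in either document receives a model-adjusted between-arm estimate.
- **That weight is not reported by arm at all.** The baseline table and the grouping of the listings show otherwise. What is missing is the summary of post-baseline weight and of its change.

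**Conclusion.** The point holds as an undeclared difference between protocol and SAP: no by-arm summary of post-baseline weight or weight change is planned for an endpoint that the protocol says will be summarised that way. The loss is one descriptive table with one scheduled post-baseline time point. It is a reporting gap in a secondary safety measure. It does not touch the primary analysis, any decision rule or the data collected.

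The conclusion assumes that the SAP is followed as written and that table specifications outside these documents do not add the summary. Whether the omission was intended cannot be told from the text.

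**What to change.** In SAP Section 8.10.3, add body weight to the sentence that plans descriptive summaries of values and change from baseline by received treatment group. Specify baseline and Week 24, and show Early Termination values separately so that they are neither dropped nor merged with Week 24. Align the opening definition with the listing sentence so that the section treats weight consistently. This restores protocol Section 10.4.3.4.

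If the sponsor prefers not to produce the summary, the omission should be declared and justified in SAP Section 10.

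Percent change, or a baseline-adjusted difference from placebo with a confidence interval, may be added but is not needed for agreement with the protocol. The cost is one phrase in the SAP and one table from data already collected, with no change to visits or procedures.
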